### **Breaking the Blind**

In the event of a medical emergency, the investigator will be able to obtain treatment assignment of each participant.

### **Sample Size**

200 patients, 100 per arm

### **Analysis**

The primary analysis will be the difference between baseline and week 48 in urine albumin/creatinine ratio (UACR) between ATP and B/F/TAF treated participants. Safety and tolerability will also be assessed.

Eight secondary statistical analyses will be performed comparing the ATP and B/F/TAF arms of the study:

- (1) HIV-1 RNA < 50 copies/mL at TW48

- (2) Differences from baseline to TW4 in EFV symptom scores (as per GS-US-292-0109)
- (3) Differences from baseline to TW48 in urine protein/creatinine ratio (UPCR)
- (4) Differences from baseline to TW48 in estimated glomerular filtration rate (eGFR)
- (5) Differences from baseline to TW48 in bone mineral density (BMD) at the hip
- (6) Differences from baseline to TW48 in BMD at the spine
- (7) Differences from baseline to TW48 in CD4 lymphocyte counts
- (8) Differences from baseline to TW48 in serum lipids

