### **Exclusion Criteria**

1. Pregnancy, breastfeeding or planned pregnancy in the next 2 years
2. Documented resistance to the components of ATP
3. Active AIDS-defining opportunistic infection or cancer
4. Cancer in past 3 years, except non melanoma skin cancer
5. Active psychotic disease or active depression that may interfere with study participation according investigator discretion
6. Any illness with a life expectancy less than 2 years
7. eGFR < 50 mL/min
8. Urine protein/creatinine > 40 mg/mmol
9. Patients who the investigator feels are unlikely to commit to the study requirements for any reason
10. Prescription drug therapy for osteoporosis (calcium and/or vitamin D is allowed)

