### **Screening**

1. Medical history (including any HIV resistance testing) and physical examination
2. Labs: CBC-D, CD4, creatinine, phosphorus, albumin, ALT, bilirubin, lipids, CD4, HIV RNA, HBsAg (if last result was negative > 6 mo ago), anti-HCV (if last result was negative > 6 mo ago), UPCR, UACR, DEXA hip and spine
3. Add HBV DNA, HBeAg and anti-HBe for all known to be HBsAg+ (if last result was > 3 mo ago)

4. Add HCV RNA for all known to be anti-HCV+, if last test was negative > 12 months ago
5. Add FibroScan for all HCV RNA+ and/or HBsAg+
6. EFV related symptom scores

Any labs performed for standard of care within 30 days of screening visit will be considered baseline results and used to determine inclusion/exclusion criteria.

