### **Study Intervention**

Randomized 1:1, double-blind treatment with ATP and placebo for B/F/TAF (control arm) or B/F/TAF and placebo for ATP (experimental arm). Study medication (two tabs, one active, one placebo) will be taken once daily at the same time of day and with the same amount of food (or not) that the patient was doing when taking ATP prior to study entry. Patients will take double-blinded study medications for 52 weeks, but the primary efficacy analysis will be based on treatment week (TW) 48 data.

At TW52, patients will be told whether they were taking ATP or B/F/TAF, and offered the option of continuing on B/F/TAF, if they were assigned to that arm, or switching to B/F/TAF if they were in the control group receiving ATP. Gilead will supply B/F/TAF to patients after TW52 until B/F/TAF is covered by the provincial formulary.

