### **Study Flow and Monitoring after Screening**

Patients whose screening lab tests are satisfactory will return within 30 days to initiate double-blinded study therapy. Repeat lab testing will not be done on the day that blinded study therapy is initiated.

Blood will be collected at TW4 ( $\pm$  7 days), TW12 ( $\pm$  30 days), TW24 ( $\pm$  30 days), TW36 ( $\pm$  30 days), and TW48 ( $\pm$  7 days) for HIV RNA.. CD4 and phosphorus will be measured at TW24 and TW48. Lipids will be done at TW48. Creatinine, ALT, and albumin will be measured at TW12, TW24, TW36 and TW48. Urine tests will be done at TW24 and TW48. Samples will be discarded once analyzed and will not be stored for future use. DEXA will be done at TW48. EFV-related symptom scores will be done at TW4.

Physical exams will be completed if needed based on symptoms. Adverse events will be assessed and treatment adherence discussed. Serious adverse events will be collected and reported to Gilead Sciences, Inc and Health Canada. In women of childbearing potential, highly effective birth control is required and pregnancy testing will be performed. Visits will be performed in clinic, via telehealth, or via telephone.

Concomitant medications will be recorded. Prescription drug therapy for osteoporosis is not allowed at enrollment. Antacids (e.g., Tums or Rolaids), the ulcer medication sucralfate, and vitamin or mineral supplements that contain calcium, iron, or zinc are to be taken at least 2 hours before or 2 hours after study drug.

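### The primary UACR comparison is worded as a change from baseline; naming baseline UACR as a covariate would gain precision at no cost (optional improvement, not an error)

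*Protocol*

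**What the plan says.** The Analysis section of the protocol defines the primary analysis as follows: "The primary analysis will be the difference between baseline and week 48 in urine albumin/creatinine ratio (UACR) between ATP and B/F/TAF treated participants". Seven of the eight secondary analyses are also worded as differences from baseline: urine protein/creatinine ("Differences from baseline to TW48 in urine protein/creatinine ratio (UPCR"), efavirenz symptom scores at week 4, eGFR, BMD at hip and at spine, CD4 count and lipids. The eighth is a yes/no virological outcome. No section names a model, a covariate or a measurement scale, and none rules one out.

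The data for an adjusted analysis are in the schedule. The Screening section lists "UPCR, UACR, DEXA hip and spine" and adds that "Any labs performed for standard of care within 30 days of screening visit will be considered baseline results". The follow-up section says "Urine tests will be done at TW24 and TW48". Allocation is 1:1 (Study Intervention), and the Sample Size section gives "200 patients, 100 per arm" with no supporting calculation.

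**The concern.** Read literally, the sentence describes a two-group comparison of week-48 value minus baseline value. Subtraction imposes a slope of exactly 1 on baseline. When a single urine ratio is measured about a year apart, the actual slope is likely to be below 1, because high first values tend to be followed by lower ones. The change score then carries baseline noise that a fitted slope would remove.

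What is at stake is precision with a fixed 100 patients per arm: a wider confidence interval and a greater chance of missing a real difference in albuminuria. Bias and type I error are not at stake.

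**Working it through.** **Inputs.** From the protocol: 100 per arm, 1:1 allocation, baseline and week-48 UACR both measured. Not in the protocol, so assumed: two-sided alpha 0.05, no dropout, correlation rho between baseline and week 48 of 0.3 to 0.9, and the ratio L of the week-48 SD to the baseline SD.

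**The plan's own figure.** The 200 patients cannot be reproduced, because no effect size, SD, alpha or power is given. That is not raised here. For orientation, 100 per arm detects (1.96 + 0.842) × √(2/100) = 0.40 SD with 80% power and (1.96 + 1.282) × √(2/100) = 0.46 SD with 90%.

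**Equal SDs (L = 1).** In units of the common variance, the variance of the treatment effect is proportional to 2(1 − rho) for the change score and to 1 − rho² for ANCOVA. The ratio is (1 − rho²) / [2(1 − rho)] = (1 + rho)/2.

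| rho | variance ratio | CI width ratio (square root) | change-score patients matching 200 with ANCOVA (200 / ratio) | ANCOVA power if the change score has 80% |
|---|---|---|---|---|
| 0.3 | 0.65 | 0.81 | 308 | 93.5% |
| 0.5 | 0.75 | 0.87 | 267 | 90% |
| 0.7 | 0.85 | 0.92 | 235 | 86% |
| 0.8 | 0.90 | 0.95 | 222 | 84% |
| 0.9 | 0.95 | 0.97 | 211 | 82% |

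**Unequal SDs.** The ratio is L²(1 − rho²) / (1 + L² − 2·rho·L). Denominator minus numerator equals (1 − rho·L)², so the ratio never exceeds 1 and reaches 1 only when the true slope rho·L is exactly 1.
- L = 1.2, rho = 0.8: (1.44 × 0.36) / (1 + 1.44 − 1.92) = 0.5184 / 0.52 = 0.997, practically no gain.
- L = 0.85, rho = 0.7: 0.69.
- L = 0.7, rho = 0.7: 0.49.

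**Simulation on the original scale.** With 100 per arm, log-normal UACR (log-SD 0.8 to 1.2, log-scale correlation 0.5 to 0.85), a true ratio of 0.75 and 4,000 trials per cell, adding the baseline covariate raised power in all nine cells, by 8 to 21 points. At log-SD 1.0 it went from 26% to 42% (correlation 0.5), 39% to 52% (0.7) and 60% to 73% (0.85). These gains exceed the table partly because the correlation is lower on the original scale: at log-SD 1.0 and log correlation 0.5 it is (e^0.5 − 1)/(e − 1) = 0.38.

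Other settings bound the gain:
- With gamma-shaped UACR it was 0 to 22 points.
- With baseline UACR capped at 3 times its median it was at most about 11 points. In one such cell (log-SD 1.0, correlation 0.6, 30% reduction) it was 68% against 69%, because trimming baseline alone pushes L above 1.
- Across the wider log-normal grid the adjusted analysis never fell more than 0.2 points below the change score, which is within simulation error.

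**Validity.** Without a true effect, rejection was between 3.8% and 5.7% for every method tried, so neither analysis has a type I error problem.

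**Cost.** One degree of freedom, from 198 to 197. With the change as outcome and baseline as covariate, the treatment estimate is identical to that from modelling the week-48 value on arm and baseline, and it is still a difference in mean UACR.

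**The case against.** The strongest objection is scope. Model, covariates and transformation are ordinary SAP content, the SAP is not at hand, and the protocol sentence is compatible with an ANCOVA of the change. That stands: nothing here is an omission or a mistake, and the adjustment may already be planned. What remains is that the literal reading of the stated primary analysis is the less precise one, and a single clause would settle it.

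The second objection is size. Apart from 100 per arm, every input is assumed, and the gain can be close to nil. That also stands, and it is why a range is given.

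Two stronger readings are tempting:
- **A reader might infer that the protocol commits to an unadjusted test on raw values.** It does not; the wording fixes neither the absence of a covariate nor the scale.
- **A reader might infer that log(UACR) should be the primary scale, with much larger gains.** If UACR is log-normal, these gains do appear: at log-SD 1.0, correlation 0.6 and a 30% reduction, power is 44% for raw change, 63% for raw ANCOVA and 88% for log ANCOVA. But the protocol says nothing about the shape of UACR. Its only urinary entry limit, "Urine protein/creatinine > 40 mg/mmol", concerns total protein. That indirectly bounds albumin but leaves its median unknown. With gamma-shaped data, log ANCOVA ranged from 10 points worse to 11 better than raw change. If only the top baseline quartile responds, raw ANCOVA had 39% power against 31% for log ANCOVA. The log scale also replaces a mean difference with a ratio and needs a rule for undetectable albumin. The documents do not support it as a default.

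**Conclusion.** The point holds as an optional gain in precision. The stated primary analysis is valid; done literally as a change-score comparison, it gives up precision that baseline data already scheduled for collection could supply. Under equal SDs and an assumed correlation of 0.3 to 0.9, the variance falls by 5% to 35%. The gain depends on how far the true baseline slope lies from 1. It can be close to nil (0.997 at SD ratio 1.2 and correlation 0.8), and in large samples it is never negative. The direction of the recommendation needs no distributional assumption; only its size depends on the unknown SDs and correlation.

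**What to change.** Unless the SAP already does so, state the primary analysis as ANCOVA of the change in UACR from baseline to TW48 on randomised arm, with baseline UACR as covariate. Report the adjusted mean difference with its 95% confidence interval. Use the same form for UPCR, eGFR, hip and spine BMD, CD4, lipids and the week-4 symptom scores, each with its own baseline.

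This should be fixed before unblinding. Participants are to be told their arm at TW52, so it is safest to do it before the first of them reaches that visit.

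The cost is one clause of text and one degree of freedom, with no extra patients, visits or samples and no change in the effect measure.

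A log scale may be considered separately in the SAP if pooled, blinded baseline values are clearly right-skewed. It would need a pre-set rule for undetectable albumin, and the result would be reported as a ratio. It is not part of the firm recommendation.

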### **Stopping criteria**

- Investigator determines it is not safe for individual to continue study treatment (including but not limited to intercurrent illness or participant noncompliance)
- Lack of study drug efficacy
  - o >100 copies/mL for two consecutive tests
- Pregnancy
- Participant request for any reason
- Discontinuation of study by Health Canada or Research Ethics Board

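### Does the protocol leave open whom the primary UACR analysis compares, and whether participants who stop study drug are still measured at week 48?

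*Protocol*

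**What the plan says.** The Analysis section of the protocol describes the primary analysis as the change in UACR from baseline to week 48, compared "between ATP and B/F/TAF treated participants". The next paragraph introduces eight secondary analyses as "comparing the ATP and B/F/TAF arms of the study".

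Study Intervention randomises 1:1 to two arms, each identified by its active drug plus a placebo for the other. It adds that "the primary efficacy analysis will be based on treatment week (TW) 48 data".

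Study Flow and Monitoring after Screening gives the visit schedule. Urine tests fall at TW24 and TW48. For bone density and lipids the text reads "DEXA will be done at TW48" and "Lipids will be done at TW48".

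Stopping criteria is a single list. It includes "Investigator determines it is not safe for individual to continue study treatment", a virologic criterion of ">100 copies/mL for two consecutive tests", pregnancy, the participant's own request, and "Discontinuation of study by Health Canada or Research Ethics Board". Nothing there says which assessments follow a stop.

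**The concern.** Two features invite worry.

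First, the primary and secondary analyses name their groups differently. A comparison of arms keeps everyone as randomised. A comparison of treated participants could be taken to mean only those still on drug, and selection after randomisation would then enter the primary result.

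Second, assessments are dated by treatment week, which has no obvious meaning once treatment has ended. The stopping list also puts the end of one person's treatment beside the end of the whole study. A coordinator might conclude that someone who stops drug has left the study and needs no week-48 visit. An analysis plan can choose an analysis set, but it cannot recover urine, blood or DEXA results that were never obtained. Some endpoints have no other post-baseline value, and the virologic criterion depends on an outcome of the trial, so the participants lost would not be a random sample.

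**Working it through.** **1. The two phrases.** Study Intervention calls the ATP-plus-placebo group the control arm and the B/F/TAF-plus-placebo group the experimental arm. Each arm is thus defined by its active drug. Participants treated with ATP and participants treated with B/F/TAF are then, in ordinary usage, the two arms. A contradiction would need some section to define treated participants as a subset, or to set an as-treated, per-protocol or completer analysis. None does. Study Design frames the trial as a randomised comparison of switching with remaining on ATP, which fits the same reading.

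**2. The visit schedule.** Post-baseline times, from Study Flow and Monitoring after Screening:

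| Measure | Times (TW) | Number |
|---|---|---|
| DEXA hip and spine | 48 | 1 |
| Lipids | 48 | 1 |
| EFV symptom scores | 4 | 1 |
| Urine (UACR, UPCR) | 24, 48 | 2 |
| CD4 | 24, 48 | 2 |
| Creatinine (for eGFR) | 12, 24, 36, 48 | 4 |
| HIV RNA | 4, 12, 24, 36, 48 | 5 |

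Four of the eight secondary analyses rest on one post-baseline measurement. For three (hip BMD, spine BMD, lipids) it is at TW48; for the fourth (EFV symptoms) it is at TW4, where a week-48 rule has no bearing. The primary endpoint has one other value, at TW24. None of these entries carries an exception for people who have stopped drug. The Analysis section dates the primary endpoint simply at week 48, without the treatment-week label.

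**3. The virologic criterion.** Counting scheduled tests only, two consecutive results above the threshold can be completed at TW12, 24, 36 or 48. Three of these four times precede TW48. This counts calendar slots; it is not a risk.

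**4. Scale.** The protocol gives 100 per arm but no stopping rate, effect size, SD, alpha or power. Everything below is therefore assumed.

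- Interval width if a fraction d of each arm is unmeasured: 1/√(1−d). For d = 0.05, 0.11 and 0.15 this is 1.026, 1.060 and 1.085.
- Detectable difference at two-sided 5% and 80% power: (1.960 + 0.842) × √(2/100) = 0.396 SD. Power at 0.396 SD with n measured per arm is Φ(0.396 × √(n/2) − 1.96), which gives 78.0%, 75.7% and 70.7% for n = 95, 90 and 80.
- If instead everyone is measured and stoppers contribute no treatment difference, the effect becomes 0.396 × (1−d). For d = 0.05, 0.10 and 0.20 that is 0.376, 0.357 and 0.317 SD, with power 75.9%, 71.3% and 61.1%.
- If a fraction q of one arm stops, is unmeasured, and differs from that arm's mean by s SD, the completer mean moves by q·s/(1−q). At q = 0.05 and s = 0.5 this is 0.026 SD; at q = 0.20 and s = 1.0 it is 0.25 SD.
- A simulation with dropout missing at random, an assumed log-UACR effect of −0.357 and an assumed correlation of 0.5 to 0.7 gave completer estimates of −0.346 to −0.351. The shift is 0.006 to 0.011, or 1.7% to 3.1% of the effect.
- For HIV RNA, 95% half-width at an assumed 97% suppression: 1.96 × √(2 × 0.97 × 0.03/100) = 0.047, or 4.7 percentage points. Treating virologic stops as missing instead of as failures would move the arm difference by about the difference in stops per 100: 0 points at 2 versus 2, 1 at 2 versus 1, 2 at 3 versus 1.

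**The case for a change.** The strongest argument for a change is that data collection belongs in the protocol. The primary analysis carries the looser of the two phrases, the stopping list does not separate leaving treatment from leaving the study, and two coordinators could act differently. The remedy would cost only a few sentences. The calculations also show that, at the extreme of 20% stopping in one arm with a 1 SD difference, the completer mean could move by 0.25 SD, which is not negligible beside a detectable difference of 0.396 SD.

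Part of this stands. There is indeed no explicit sentence on assessment after a stop, and the list does mix individual and study-level stops. The rest does not carry. The loss of data is inferred from silence, while the schedule as written points towards continued measurement. The 0.25 SD figure needs heavy stopping confined to one arm, no measurement of those who stop, and a large difference in their change; none of these is in the protocol. The endpoints most exposed to a missed week-48 visit (BMD and lipids) are already compared by arm, so the primary wording does not affect them. How a virologic stop is scored in the HIV RNA analysis is a normal matter for an analysis plan.

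**Conclusion.** The concern does not call for a change. The difference in wording is loose drafting, not two populations, and the schedule followed as written still gives a comparison of the randomised arms with week-48 data sought from everyone. The silence on assessment after a stop is a missing detail that investigators and analysts can fill sensibly: keep measuring those who have not withdrawn consent, and analyse by randomised arm. Writing that down would do no harm, but it would correct no rule that gives a wrong result.

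The size cannot be derived from the protocol. At assumed losses of 5% to 15%, intervals widen by 2.6% to 8.5%, as they would in any trial with that attrition. The missing-at-random simulation puts the shift in the UACR estimate at about 3% or less. This conclusion rests on reading the treated participants as the two arms and the week-48 schedule as applying to all. It would need to be revisited if the analysis plan, which was not available, restricted the primary analysis to participants still on drug.

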### **Safety Analysis**

Investigator will review data and safety information annually including adverse events, efficacy lab results, and safety lab results.

### **Ethical Considerations**

This study will be conducted according to Canadian and international standards of Good Clinical Practice for all studies. Applicable government regulations and University of Alberta research policies and procedures will also be followed.

This protocol and any amendments will be submitted to the University of Alberta HREB for formal approval to conduct the study. The decision of the HREB concerning the conduct of the study will be made in writing to the investigator.

All subjects for this study will be provided a consent form describing this study and providing sufficient information for subjects to make an informed decision about their participation in this study. This consent form will be submitted with the protocol for review and approval by the HREB. The formal consent of a subject, using the HREB-approved consent form, will be obtained before that subject is submitted to any study procedure. This consent form must be signed by the subject or legally acceptable surrogate, and the investigator-designated research professional obtaining the consent.
